c. Statistical plan including sample size justification and interim data analysis.

Sample Size: As a pilot RCT, we aim to enroll a convenience sample of ~1.5 patients/month, for a total of 54 patients (based on 36 months of recruitment; see Timeline-Candidate Statement). Extensive experience enrolling ARF patients in prior studies by our group^{10,121,125-127} suggests this rate is feasible for a K-23 award at this study site. We expect an overall <15% missing completion rate due to mortality and loss to follow-up (in our prior study of >500 ARF survivors, loss to follow-up was 2% with 7% mortality at 6 months¹²⁵), thus, we expect 54 patients to complete the intervention. With 54 participants (27 in each group), assuming 5% alpha, 80% power and HAD SD of 4.2 points based on our prior research in ARF survivors^{89,90}, for our secondary aim of efficacy, we can detect a 3.1 point difference in HADS score between the 2 treatment groups, which approximates HAD's 2.9 point minimum important difference (MID) in ARF survivors.¹²⁸ This proposed enrollment rate and sample size is consistent with existing pilot/feasibility trials in ARF research.^{101,129,130}

Statistical Analysis

Hypothesis 1a: *A 12-week BA-R intervention in ARF survivors will be feasible, as demonstrated by an average accrual rate of 1.5 patients per month, completion of ≥80% of the intervention phone calls, and ≤15% of enrolled patients lost to follow-up for outcomes assessments at end of the 12-week intervention.* We will assess the total number of intervention phone calls completed per patient as a proportion of the number of intervention phone calls each patient is intended to complete (i.e., 9 intervention calls – weekly during first 6 weeks and bi-weekly for second 6 weeks of the 12-week protocol). We also will assess total number of intervention phone calls completed by all study participants as a proportion of total intervention phone calls expected in the study. We will calculate the number of patients completing the 12-month follow-up session as a proportion of the number of patients enrolled to measure loss to follow-up.

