Hypothesis 1b: *At the end of the 12-week BA-R intervention, ARF survivors in the BA-R versus “usual care” group will demonstrate decreased depressive symptoms, less impairments in physical function and quality of life, and reduced healthcare utilization.* Analyses will follow a modified intention-to-treat principle and a 2-tailed p<0.05 is statistically significant. Patient mortality is expected to occur infrequently (see Sample Size above) and not to differ by treatment vs. control group; therefore, all analyses will be conducted for 12-week survivors only. The analysis will include separate comparisons of the effect of the BA-R intervention vs usual care control on each of the blinded outcomes in Table 4. These analyses will estimate the average treatment effect, i.e. the difference in the mean 12-week outcome comparing the BA-R intervention to the usual care control, using the precise locally efficient augmented simple estimator (PLEASE) described in Colantuoni and Rosenblum[REF: 135]. This method for estimating the average

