treatment effect is similar to the analysis of covariance (ANCOVA) approach in that it incorporates the baseline outcome (if measured) which, if correlated with the 12-week outcome, can improve the precision of the estimated average treatment effect [Ref 134]. This method also accounts for more general patient drop-out models than the ANCOVA approach. Specifically, the ANCOVA approach is valid under completely at random drop-out, whereas the PLEASE is valid under missing at random drop-out, i.e. when patient drop-out differs by treatment group or across levels of the baseline outcome or other measured variables at baseline. The PLEASE requires a priori specification of three models: an outcome regression model (fit separately for each treatment group) that will include age, gender and the baseline outcome (if measured), a propensity score model that will include age, gender and the baseline outcome (if measured) and a drop-out model (fit separately for each treatment group) that will include age, gender, and the outcomes measured at baseline (HADS, Brief Cope, CD RISC, BADS). As exploratory analyses, the 12-week outcomes (e.g. HADS scores) will be summarized (summary statistics including counts of missing values and histograms) and the correlation of the baseline (if appropriate) and 12-week outcomes will be computed, separately by treatment arm. Patient mortality, drop-out and missing data will be described for all variables, separately for treatment vs control groups. Patient characteristics will be compared between those with vs. without missing outcomes (due to drop-out and missing values).¹³⁶⁻¹³⁸

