A series of secondary analyses will be conducted to improve our understanding of the changes in the outcomes over time under the BA-R intervention and usual care control and to improve the design of subsequent larger randomized trials evaluating the effect of the BA-R intervention. Specifically, the outcomes over time within each treatment group will be visualized using spaghetti plots to display each patient's data with the mean outcome over time trajectory over time highlighted. Longitudinal linear regression models for the longitudinal outcomes (i.e. baseline, 6-week and 12-week outcomes) will be constructed that account for time (factor), treatment and the interaction of treatment and time. These longitudinal models will be fit using weighted least squares and will allow for the possibility that the variance in the outcomes can change over time and that outcomes measured on the same patient over time may be correlated. In addition, we will explore the prognostic ability of other baseline variables (e.g. age, sex and history of depression) for the 12-week outcomes using the method described by Colantuoni and Rosenblum.¹³⁵ Specifically, we will compute the leave-one-out cross-validated relative R-square which compares the R-square obtained when modeling the 12-week outcomes as a function of selected baseline variables, separately for each treatment arm, to that obtained by predicting the 12-week outcomes with the treatment arm specific mean. The statistic ($1 - 1/\text{relative R-square}$) is roughly the sample size reduction that can be achieved if the selected baseline variables are incorporated into an adjusted treatment effect estimator compared to using an unadjusted estimator. This assessment will provide relevant information to improve the design and analysis of subsequent larger randomized trials evaluating the effect of the BA-R intervention; specifically, by informing which additional prognostic baseline variables to include in the ANCOVA approach described above to further improve the precision of the estimated treatment effects.

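### The secondary longitudinal model leaves baseline means free by arm, so its week-6 and week-12 contrasts do not use the baseline outcome efficiently

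*Combined protocol and SAP*

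**What the plan says.** The main efficacy analysis for Hypothesis 1b (Section 7c) targets "the difference in the mean 12-week outcome comparing the BA-R intervention to the usual care control". It uses PLEASE, chosen partly because it "incorporates the baseline outcome (if measured) which, if correlated with the 12-week outcome, can improve the precision". It has no week-6 estimand.

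The plan then adds secondary work: "A series of secondary analyses will be conducted to improve our understanding of the changes in the outcomes over time". This includes "Longitudinal linear regression models for the longitudinal outcomes (i.e. baseline, 6-week and 12-week outcomes", with terms that "account for time (factor), treatment and the interaction of treatment and time". The fit allows the variance to change over time and allows that "outcomes measured on the same patient over time may be correlated". The plan names no constraint on the baseline means and no baseline covariate. It does not say which contrast is the treatment effect. In Table 4, whose layout is broken in the text available, week 6 is marked only in the depressive-symptoms row.

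**The concern.** Baseline is one of the modelled responses, so the treatment main effect gives each arm its own baseline mean. Two arm contrasts can then be read from the model: the difference at week 6 or week 12, or the treatment-by-time interaction, which is a difference in change from baseline. The first is unadjusted. The second subtracts the whole baseline difference, which over-corrects whenever the correlation is below 1 and variances are equal.

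Two things are at stake. The week-6 comparison would be less precise than the collected data allow. The trial could also report two 12-week effects, one baseline-adjusted and one not, that disagree only because the arms differed by chance at baseline. These analyses are meant to inform later trials, so both matter somewhat.

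**Working it through.** **Inputs.** From the sample-size paragraph of Section 7c: 27 per arm, HADS SD 4.2, alpha 5%, power 80%. From Hypothesis 1b: two-sided testing. Assumed, because the documents do not give it: baseline to follow-up correlation r between 0.2 and 0.7, the same for all pairs of visits, with SD 4.2 at every visit.

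**The plan's own figure.** The SE of an unadjusted difference is 4.2 × √(2/27) = 1.143. The detectable difference is (1.960 + 0.842) × 1.143 = 3.20 points (3.26 with the t distribution), against 3.1 stated. This small gap is a separate matter. It confirms that the stated figure is close to an unadjusted two-sample calculation.

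**Why correlated errors do not repair the planned model.** Time as a factor, treatment and their interaction give one free mean per arm and visit. With complete data, generalised least squares then returns the observed means whatever the correlation.

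**Variances.** Let d0 and dt be the arm differences at baseline and at follow-up. In units of 1.143²:
- visit difference, dt: 1
- difference in change, dt − d0: 1 + 1 − 2r = 2(1 − r)
- equal baseline means, dt − r·d0: 1 + r² − 2r² = 1 − r²

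The third is never larger than either of the others.

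| r | SE visit | SE change | SE equal baseline | visit excess | change excess |
|---|---|---|---|---|---|
| 0.2 | 1.143 | 1.446 | 1.120 | √(1/0.96): 2% | √(1.6/0.96): 29% |
| 0.3 | 1.143 | 1.353 | 1.090 | √(1/0.91): 5% | √(1.4/0.91): 24% |
| 0.5 | 1.143 | 1.143 | 0.990 | √(1/0.75): 15% | √(1/0.75): 15% |
| 0.7 | 1.143 | 0.885 | 0.816 | √(1/0.51): 40% | √(0.6/0.51): 8% |

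**Small samples.** The adjustment slope must be estimated. In 20,000 simulated trials per value of r, the adjusted SE was 1.105 (r = 0.3), 1.002 (0.5) and 0.825 (0.7), about 1% above the table. At r = 0 it was 1.151 against 1.139 unadjusted, a loss of about 1%.

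**Dropout.** Suppose 15% of each arm gives baseline only, and r = 0.5. The visit difference from the planned model has SE 1.216, against 1.240 for complete cases, so it does borrow a little from baseline. The equal-baseline model has SE 1.074. The excess is 1.216/1.074, or 13%.

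**Disagreement at 12 weeks.** The visit difference exceeds the adjusted estimate by r·d0. The change contrast falls below it by (1 − r)·d0. For a chance baseline imbalance of one standard error (1.143 points) and r = 0.5, each shift is 0.5 × 1.143 = 0.57 HADS points, in opposite directions.

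**The case against.** The strongest defence is that nothing inferential rests on this model. Its stated purpose is to describe change over time and help later design. A mean model with one free value per arm and visit suits that, and showing the observed baseline by arm is reasonable. Hypothesis 1b concerns the end of the intervention, where PLEASE already adjusts for baseline. The plan also reports the baseline to 12-week correlation and a cross-validated measure of what baseline variables could save. All of this stands, and it makes the point a small one. It does not provide an efficient week-6 comparison.

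A second objection concerns timing. Section 4a has patients randomised once they are home. Table 1 places the home questionnaires ahead of the intervention, but not clearly ahead of randomisation. Participants know their allocation, so a self-report taken after it could already differ by arm. This also stands and makes the fix conditional. The same question arises for the baseline adjustment in PLEASE. In addition, analyses are limited to patients alive at 12 weeks, so equal baseline means in that set rely on the plan's own expectation that mortality will be infrequent and similar in both arms.

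A reader might infer that the model ignores baseline altogether. It does not. The interaction uses baseline as a change score, and under dropout the correlated fit borrows from it. Only the visit difference with complete data makes no use of it.

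**Conclusion.** The point holds as an optional gain in precision for a secondary analysis. As listed, the model's arm contrasts are less precise than baseline-adjusted ones by 2% to 40% in SE for the visit difference and 8% to 29% for change, over r from 0.2 to 0.7. These figures assume equal variances, equal correlations and complete data. The true r is unknown until the trial reports it. If r is near 0, the visit difference loses nothing.

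The consequence falls mainly on the week-6 HADS comparison. Two stronger readings are not supported. The main 12-week efficacy result is not weakened, because it comes from PLEASE. Nor is the trial too small on this account: at r = 0.5 the variance ratio is 1/0.75 = 1.33, but the sample size does not rest on this model and the primary outcome is feasibility.

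**What to change.** Add one sentence to the secondary analyses in Section 7c. For treatment effects from the longitudinal model, drop the treatment main effect at baseline, so that the arms share one baseline mean. Keep time, the treatment-by-time terms at weeks 6 and 12, and an unstructured variance and correlation. Name those two treatment-by-time terms as the reported contrasts. In practice it is equivalent to model weeks 6 and 12 with baseline as a covariate.

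State in Section 4a whether the baseline questionnaires come before randomisation. If they do not, do not impose equal baseline means, and say which contrast will be reported. Observed baseline means by arm can still appear in the descriptive plots.

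The cost is this wording and the check on timing. No new data are needed.

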If clinically important, unanticipated adverse problems or clinically important study-related, serious adverse events occur, they will be recorded on a designated case report form. All events that are serious and unanticipated, or study-related and adverse will be reported to IRB within the required reporting timeline.

Definitions:

Adverse event: any untoward medical occurrence associated with the use of a drug in humans, whether or not considered intervention related.

Serious Adverse Event (SAE) - an adverse event will be considered "serious" if, in the view of the investigator, it results in any of the following outcomes: death, a life-threatening adverse reaction, re-hospitalization, a persistent or significant incapacity, or substantial disruption of the ability to conduct normal life functions.

Suspected Adverse Event - any adverse event for which there is a reasonable possibility that the drug caused the adverse event.

Unexpected Adverse Event - an adverse event or suspected adverse reaction is considered "unexpected" if it is not listed in the investigator brochure or is not listed at the specificity or severity that has been observed; or, of an investigator brochure is not required or available, is not consistent with the risk information described in the general investigational plan or elsewhere in the current application.

d. Legal risks such as the risks that would be associated with breach of confidentiality.

All patient data will be confidential and secure due to physical and electronic data security measures, including locked offices and locked filing cabinets for records and computers, and password protection for computers and electronic data storage. All participant-identifying information will be removed from the dataset before analysis. Only study staff who are required to, will know the linkage between the unique identifier and participant-identifying information. We will keep all patient information confidential in

accordance with Public Health Services Act (42 USC 299a-1(c)). There is low risk of a breach of confidentiality.

e. Financial risks to the participants.

There are no expected financial risks to the participants.

9. Benefits

a. Description of the probable benefits for the participant and for society.

Currently, there are few therapeutic options with proven, or potential, efficacy to prevent or minimize depressive symptoms in acute respiratory failure survivors. Hence, this study offers important new knowledge through testing the BA-R intervention in this patient population. The BA-R intervention has been demonstrated to improve depressive symptoms in other chronically ill populations. Given the prevalence of depressive symptoms in acute respiratory failure survivors, gaining information regarding the feasibility and potential benefit of BA-R in this pilot study has great importance. This therapy is especially ideal in acute respiratory failure survivors because it can be delivered via phone with only 2 home visits required by PT and OT. The potential benefits far outweigh the minimal potential risks of this intervention.

If successful, the use of BA-R therapy may improve post-acute respiratory failure depressive symptoms, improve physical function and decrease healthcare utilization while improving quality of life.

10. Payment and Remuneration

a. *Detail compensation for participants including possible total compensation, proposed bonus, and any proposed reductions or penalties for not completing the protocol.*

For each assessment during the study, both intervention and control group patients will be remunerated as follows: \$25 for baseline assessment prior to intervention period, and \$50 for assessment at the end of the intervention period.

In addition, the intervention group only will be remunerated \$100 for completion of all intervention visits.

11. Costs

a. Detail costs of study procedure(s) or drug (s) or substance(s) to participants and identify who will pay for them.

There will not be any additional costs to participants beyond routine financial obligations for their hospitalization.

References

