BA-R Phone intervention: WEEKS 1-6: Approximately one week after the OT home visit, and weekly thereafter throughout the initial 6-week intervention period, the participant will receive a phone call from the OT. During each call, the OT will query participants' success with BA-R goals and adherence barriers (e.g., need for assistance, lack of motivation). If goals are met, the OT will help the participant establish goals for the next week, and these goals along with an action plan will be delineated in a Progress Worksheet. If the goals are not met, the OT will assist the participant in addressing barriers as detailed above. WEEKS 7-12: At about 6 weeks, the PT will conduct a second audiovisual visit. Given current restrictions (as of March 13, 2020) due to the coronavirus pandemic, home visits have been converted to audiovisual visits. The PT will assess if the exercise level should be changed (e.g., increase or decrease intensity/duration). The OT will review progress on the action plan. Depending on achievement, participant preferences, and recovery trajectory, the OT and participant will develop new goals for participating in valued activities over the next 2 weeks. An action plan to achieve these goals will be entered into the Progress Worksheet. Phone calls will continue every 2 weeks during weeks 8-12. This will allow the OT to determine whether the participant has mastered the concept of goal setting and can stay on track with less contact.

Usual Care Control Group: Participants randomized to this arm will receive usual care only, in order to reflect a real-world comparator. This group is expected to include primary care, possibly outpatient physical therapy, mental health, and home health nurses. As per Table 2, these data will be collected to describe usual care received by the control group. These same data also will be collected for the intervention group to characterize usual care received outside of the BA-R intervention. These data will be recorded from the time of enrollment until end of the intervention.

Table 2: Mental Health & Physical Rehabilitation "Usual Care" Data Collection (both Intervention & Control Group)

Mental Health Care

1. **Psychiatric pharmacotherapy** (e.g., anti-depressant, anti-anxiety meds)
 - a. Including drug name, dose, frequency & duration of use
2. **Provider Visits*** (including psychotherapy, counselling and support)
 - a. Number, frequency & duration
 - b. Type,** frequency & duration of intervention

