Participants cannot be blinded to the intervention. Treatment allocation will be concealed, except to staff performing the intervention. Research staff performing all outcome assessments will be blinded (except [name] who will not be masked to treatment assignment and will administer the SCID). Patients will be instructed (using standard language, as per prior research)¹⁰¹⁻¹⁰³ not to discuss treatment allocation with staff prior to each assessment. Adequacy of blinding will be assessed by asking assessors to indicate if they were un-blinded and for their “best guess” of patients’ treatment allocation.¹⁰³

d. Justification of why participants will not receive routine care or will have current therapy stopped.

All study participants in the usual care group will receive routine care. Participants in the intervention group will receive the intervention in addition to routine care.

e. Justification for inclusion of a placebo or non-treatment group.

We chose to compare our intervention against a “usual care”, rather than a sham control that would attempt to control for extra attention but does not represent real-world usual care. We will measure usual care for both control and intervention groups (Table 2). Participants in the usual care group will not be deprived of any known potential benefits by not being included in the intervention group (no proven benefit yet in the ARF population).

f. Definition of treatment failure or participant removal criteria.

Participants will only be removed from the study if they withdraw consent.

g. Description of what happens to participants receiving therapy when study ends or if a participant’s participation in the study ends prematurely.

If a participation in the study ends prematurely, the participant will continue to receive usual care. Ending the intervention prematurely does not pose any harm to the participant.

5. Inclusion/Exclusion Criteria

Table 3. Eligibility Criteria

Inclusion Criteria:

≥18 years old

Living at home before the current admission (not in a facility)

Acute respiratory failure managed in the ICU ≥ 24hrs (≥1 of the following):

- 1) Mechanical ventilation via an endotracheal tube or tracheostomy > 12hrs (and not ventilator-dependent before admission) OR
- 2) Non-invasive ventilation (CPAP, BiPAP) > 4 hours in a 24 hour period provided for acute respiratory failure (not for OSA or other stable use) OR
- 3) High flow nasal cannula with FiO₂ ≥ 0.5 for ≥4 hours in a 24hr period

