8. Risks

a. Medical risks, listing all procedures, their major and minor risks and expected frequency.

1) Depression: Participants will be asked questions about depression using the PHQ-8, HADS and the SCID. While asking questions, we may detect that the patient has worsening depressive symptoms.

2) Breach of confidentiality: We will be collecting data about the participant, and hence, there is a risk of breach of confidentiality.

b. Steps taken to minimize the risks.

[figure not shown]
Depression (PHQ-8, HADS and SCID): All potential participants who have worsening depression symptoms will be informed that they may be depressed and advised to consult with their health care provider.

If there is any potential concern regarding safety of a participant, a physician on our study team will become involved. The research assistant will be instructed to take the steps outlined in Figure 2 below.

- Complete a Serious Adverse Event Report (SAE) form documenting the outcome of this questionnaire and subsequent action taken.
- If unsure about the patient's risk, contact a study physician to notify them immediately and discuss action to take.

Figure 2. Suicide Risk Management Protocol

Suicide Risk Management Protocol for BA-R Pilot Study

Adapted from Suicide Risk Management Protocol in Post-Cardiac Arrest Survivors: Development, Feasibility, and Outcomes by RA Bucy et al Ann Am Thorac Soc. 2016 Dec 16; Article in Press)

*Suicide prevention helpline by state:

State Number	Local County/City wise
Maryland [name] http://www.suicide.org/hotlines/maryland-suicide-hotlines.html	
 • Baltimore • Baltimore Crisis Response- [contact] • Suicide Prevention [contact] • Columbia [contact] • Frederick [contact] • Glen Burnie (Serving Baltimore County) [contact] • Hyattsville (Serving Anne Arundel, Calvert, Charles, Montgomery, Prince George's & St. Mary's Counties) [contact] • Rockville [contact] [contact] TTY • Salisbury [contact](HELP) [contact]
Washington D C [name] (Arlington)	
 • Arlington [contact]
Virginia [name] For DC Metropolitan area http://www.suicide.org/hotlines/virginia-suicide-hotlines.html	
 • Arlington [contact] • Dumfries[contact] • Richmond [contact] • Roanoke[contact] (8:15 am to midnight) • Winchester [contact]

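### The recording rule leaves anticipated, unrelated serious events off the event form while questionnaire outcomes go onto an SAE form, so any SAE summary would be incomplete and mixed

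*Combined protocol and SAP*

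**What the plan says.** Section 8 (Risks), in the event-reporting paragraph that precedes 8d, sets what goes on the form: if clinically important "unanticipated adverse problems or clinically important study-related, serious adverse events occur, they will be recorded on a designated case report form". The next sentence sets a different rule for the ethics board: "All events that are serious and unanticipated, or study-related and adverse will be reported to IRB within the required reporting timeline".

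Under the definitions that follow, an adverse event is serious if, in the investigator's view, it results in "death, a life-threatening adverse reaction, re-hospitalization, a persistent or significant incapacity, or substantial disruption of the ability to conduct normal life functions". An adverse event is itself "any untoward medical occurrence associated with the use of a drug in humans, whether or not considered intervention related", although Section 6 lists no drug, substance or device. The definitions cover *unexpected* (without a brochure, not in keeping with the application's risk information). They do not cover *unanticipated*, which is the word the recording rule uses.

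Section 8b lists steps for the research assistant when a safety concern arises around the depression questionnaires. One is: "Complete a Serious Adverse Event Report (SAE) form documenting the outcome of this questionnaire and subsequent action taken". The stated trigger is any potential concern about a participant's safety.

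Of the control arm, Section 4a says: "Participants randomized to this arm will receive usual care only, in order to reflect a real-world comparator". Section 4c blinds the staff who assess outcomes, "except [name] who will not be masked to treatment assignment and will administer the SCID". Table 4 collects facility admissions and survival status at the end of the intervention. The analysis for Hypothesis 1b compares the blinded Table 4 outcomes among those alive at 12 weeks and describes mortality by arm.

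**The concern.** A two-arm pilot that is meant to inform a larger trial will be asked what harm it saw. If the answer is compiled from the event forms, it depends on two judgements, whether an event was anticipated and whether it was study-related, and not only on what happened. The first term is undefined. The second does not apply equally to the arms: a BA-R participant follows exercise advice and activity goals from the study, whereas a control participant receives only study assessments. The visible text does not say who judges relatedness. Meanwhile the SAE forms can carry questionnaire outcomes that meet none of the seriousness criteria. At stake is whether the harms record can be read as a list of the serious events that occurred.

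**Working it through.** The documents state no SAE rate or count, so there is no figure to reproduce. The check sets the rules side by side and then uses illustrative arithmetic.

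**1. The two rules applied to every type of event** (clinically important events assumed)

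| Serious | Unanticipated | Study-related | Event form | IRB |
|---|---|---|---|---|
| yes | yes | yes | yes | yes |
| yes | yes | no | yes | yes |
| yes | no | yes | yes | yes |
| yes | no | no | **no** | no |
| no | yes | yes | yes | yes |
| no | yes | no | yes | no |
| no | no | yes | **no** | yes |
| no | no | no | no | no |

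Row 4 is the gap: a serious event that is anticipated and unrelated is never put on the form. Row 7 is a smaller mismatch: such an event goes to the IRB, but the form rule does not require it to be recorded.

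**2. What falls in row 4 depends on the undefined word.** On its ordinary meaning, death is anticipated, because the sample-size section cites 7% mortality at 6 months, and re-hospitalization arguably is too. Such events then reach the form only if judged study-related. If the word is read through the definition of unexpected, Section 8a lists only worsening depression and breach of confidentiality, so many re-hospitalizations would be recorded in both arms.

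**3. What Table 4 covers of the five seriousness outcomes**
- Death: covered by survival status at the end, and described by arm.
- Re-hospitalization: covered at the end, but compared among 12-week survivors, so admissions of those who die drop out. Those lost to follow-up are not asked. The feasibility criterion tolerates 15% loss; 8 of 54 (8/54 = 14.8%) would still meet it.
- Life-threatening reaction: no item.
- Incapacity, and substantial disruption of normal life: function is measured as a score at the end, but these are not collected as events.

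**4. Deaths.** Assuming a constant hazard, 12-week mortality is 1 − (1 − 0.07)^(12/26) = 0.033. Expected deaths are 27 × 0.033 = 0.9 per arm, about 1.8 in all. Survival status would pick these up whether or not a form is filed.

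**5. Could the arms differ on the form?** Recorded events per arm = 27 × true rate × recording probability. Assume the same true rate in both arms, between 10% and 30%, which is 2.7 to 8.1 participants per arm. These rates and the recording probabilities below are assumptions.

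| Recording probability, BA-R v control | Recorded, BA-R | Recorded, control | Ratio |
|---|---|---|---|
| 20% v 20% | 0.5 to 1.6 | 0.5 to 1.6 | 1 |
| 30% v 10% | 0.8 to 2.4 | 0.3 to 0.8 | 3 |
| 30% v 5% | 0.8 to 2.4 | 0.1 to 0.4 | 6 |

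The ratio is simply the ratio of the recording probabilities. The documents give neither, so both the presence and the size of an imbalance are unknown. The under-count within each arm does not need the probabilities to differ.

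**6. The questionnaire form.** The Section 8b trigger is any potential safety concern. The Section 8 definition needs one of five outcomes. The visible text does not connect the two.

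**The case against.** The strongest reply is that the rule is the same for both arms. A reader might infer that usual-care events are virtually shut out. That describes the study-related route but not the unanticipated route, which takes no account of arm and on one reading admits many control re-hospitalizations. This stands. It also shows that the same event is kept or dropped according to how an undefined word is read.

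A reader might also infer that a real excess of re-hospitalizations in one arm would disappear. It would not: admissions are a Table 4 outcome, so the planned comparison would show it, apart from participants who die or are lost. Nor is any SAE table or test by arm planned in the visible text, so the plan cannot be charged with a misleading SAE comparison. Both points stand. What remains is the serious events that Table 4 does not ask about, and any harms summary that draws on the forms.

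It is also tempting to argue that the nine BA-R calls bring more events to light. The sentence in Section 4b on weekly and fortnightly telephone contact follows one about all participants, and it is unclear whether it includes controls. No contact count by arm can be relied on.

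Finally, completing an SAE form is not the same as classifying an SAE, since seriousness is left to the investigator. Questionnaires go to both arms, so this instruction does not by itself create an imbalance. The suicide-risk flow chart and the text immediately before the event-reporting paragraph were not available to this review and may hold a threshold or further rules. The need to reconcile 8b with the definition stands on the text that can be read.

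**Conclusion.** The concern holds as a point about completeness and consistency. Followed exactly, the rule omits serious events that are anticipated and unrelated, turns on an undefined term, and uses a relatedness route that is largely closed to control participants. Questionnaire outcomes can enter the SAE file without a visible seriousness test. Any SAE summary built on these forms would be incomplete and mixed.

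An imbalance between arms is possible but cannot be quantified from the documents; the ratios of 1 to 6 rest entirely on assumed recording probabilities. The documents do not support the stronger conclusions that control events are hardly ever recorded or that a planned comparison by arm is misleading. The primary outcome, feasibility, is unaffected. The conclusion assumes that the unavailable text adds no wider recording rule.

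**What to change.** - Record every event that meets the seriousness outcomes in Section 8, in both arms, from randomisation to the final assessment, regardless of relatedness or expectedness.
- Elicit these events with the same fixed questions at the week-6 and final assessments, asked by the blinded assessor and not by the unmasked SCID interviewer. Table 4 schedules a week-6 assessment but Section 4b does not describe it, so confirm that it is made in both arms.
- Mark events learned only through OT or PT contacts, so that they can be listed separately.
- Use relatedness and expectedness only to decide IRB reporting. Define unanticipated or replace it with the defined term, and reword the adverse event definition, which refers to a drug.
- Reconcile Section 8b with the Section 8 definition. Log questionnaire flags separately and count one as an SAE only if it meets that definition. This concerns recording only and leaves the safety steps as they are.

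The cost is a form page and a few questions at assessments already scheduled. The downside is slightly longer calls and more events listed. Treatment, sample size and the primary outcome do not change.
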